12.1 Risks

12.1.1 Potential Risks

Potential risks of the behavioral and motor tasks are minimal and easily addressed (see below). The major risk associated with genetic testing is a loss of confidentiality.

There are well-known but rarely encountered risks from brain imaging with MRI and CT, or standard X-Ray exams. For the former, the risks include contrast administration (not relevant here), dislodging a metal object in the patient, interfering with an implanted device (e.g., pacemaker) and moving metallic objects in the scanner room. Protocols to deal with these issues are described below. The major risk from CT or X-rays is exposure to small amounts of ionizing radiation.

A variety of potential risks from repetitive TMS, including daily TMS administrations, have been identified (see 106 for a recent review); these include the following:

1. Seizures: Seizure induction represents the most serious known risk of TMS. The risk of seizures is quite low in subjects receiving single pulse TMS. Based on an extensive review of the literature, guidelines have been developed that specify the number of stimulations that may safely be given as a function of stimulus intensity (% of Motor Evoked Potential) and frequency of stimulation (138; see also Rossi et al, 2009). Using these guidelines there have been no published reports of seizures or evidence of after-discharge or spread of excitation in normal subjects receiving low-frequency repetitive TMS. We will adhere to the published guidelines.

It is plausible that a TMS-induced seizure could adversely affect a patient's ability to obtain health insurance, obtain or retain a driver's license, or obtain or retain employment. For example, physicians in the state of Pennsylvania are required to report patients who have experienced seizures to the Department of Transportation. Because seizures induced by TMS are considered to be provoked single events that do not convey an additional risk of developing epilepsy, patients who have a seizure due to TMS would presumably be considered exempt from the restrictions on driving that the Department of Transportation sometimes enforces on other seizure patients. If such a problem were to arise, [name] or [name] would contact the appropriate institutions, explain the circumstances under which the patient experienced a provoked seizure, and express our professional opinion that a single TMS-induced seizure does not put a patient at significantly higher risk for spontaneous future events. Patients will also be provided with a letter stating that their seizure was experimentally induced. We cannot, however, guarantee patients that our advocacy on their behalf will convince employers, insurers, or other organizations that they are not at risk for future seizures.

2. Effects on Cognition: A number of studies have attempted to identify adverse neuropsychological consequences of TMS. Several such studies demonstrated a trend for performance to be better on cognitive measures after TMS (see 43). Two studies demonstrated minor adverse effects of TMS lasting up to one hour (Greenberg et al [cited in 128]; 36). Both studies, however, employed involved rapid repetitive TMS with stimulus parameters that would no longer be considered acceptable in light of current guidelines.

3. Effects on Mood: Dysphoria with crying has been induced after left prefrontal stimulation (92). In contrast, high frequency stimulation of right prefrontal cortex may transiently improve mood. TMS has been shown to be a safe and effective treatment in patients with depression that was unresponsive to other types of treatment. There are no reports of lasting changes of mood after single pulse or low frequency TMS.

8. Kindling: Kindling is a process by which repeated administration of an initially subconvulsive stimulus results in a progressive intensification of induced neuroelectrical activity resulting in a seizure. This has not been reported with TMS and appears unlikely for several reasons. Kindling is most readily obtained with high rate repetitive stimulation (e.g., 60 Hz), requires pulse duration of 1 ms (longer than that of TMS) and is easiest to produce in the amygdala and hippocampus. Kindling of neocortex in animal models of epilepsy is very difficult to achieve. There is no evidence that kindling can be produced by TMS.

9. Exposure to Magnetic Fields: The maximal field strength generated by commercially available stimulators such as the MagVenture machine to be used in our lab is in the 2 Tesla range. The field is induced for a brief period only and the strength of the field falls off rapidly with distance from the coil. There is no evidence of adverse effects from magnetic field exposure during TMS.

As the proposed studies involve TMS to subjects with brain lesions it is important to note that TMS has been used extensively in subjects with brain pathology since the 1990s (e.g., 26). Significant adverse effects in subjects with stroke are rare. For example, Hoyer and Celnik (53) reviewed studies in which TMS was administered to either the lesioned (13 studies) or contralesional (12 studies) hemisphere for treatment of hemiparesis. No significant adverse effects were reported in these studies; in many of the studies (e.g., 61), TMS was administered with high frequency stimulation over the lesioned hemisphere, a procedure that is generally considered to be more likely to be associated with adverse effects than the 1 Hz stimulation we propose.

Also of relevance is that rTMS has been administered for the treatment of aphasia to over 250 subjects in more than 20 studies, including studies done at Penn by our group; while most studies involved 1 Hz stimulation over the contralesional hemisphere (as we will be doing), several studies employed more aggressive procedures such as high frequency repetitive stimulation over the lesioned hemisphere (e.g., 62; 126). No significant side-effects were reported in any of the studies, including studies where TMS was administered in 10 daily sessions; furthermore, there is no report of an aphasic subject withdrawing from a study because of adverse effects. Thus, on the basis of data reported to date, we believe that the procedures to be employed in this study are safe in subjects with stroke and aphasia.

Under the AD Sub-Study, the decision to stimulate at 10 Hz is motivated by the fact that several studies demonstrating benefit on the ADAS-Cog in subjects with AD employed this frequency (e.g., 149, 150, 164, 170, 171). We note that the stimulation parameters that we

propose are within the guidelines proposed by Rossi et al. (106). Rapid repetitive TMS of the type that we propose to employ has been used in at least 11 studies with subjects with Alzheimer Disease; no seizures or other major adverse events have been reported.

Finally, we note that TMS with normal subjects and subjects with stroke (e.g., protocol #826841) has been considered to be non-significant risk at Penn.

12.1.2 Adequacy of Protection Against Risks

Behavioral and Motor Tasks: To protect against fatigue subjects will be permitted to rest or discontinue testing at any time. Should subjects appear to be made anxious by the tasks, testing will be terminated. Subjects will be told that they are free to withdraw from the testing at any time. The PI is not aware of any significant adverse effect from behavioral or motor testing of the type proposed in more than 30 years of work with brain-lesion subjects.

Genetic Testing: See the above "Genetic Testing" section

Brain Imaging: No contrast agents will be administered. The major risk from MRI is that the strong magnetic field will dislodge a metallic object inside the subject's body (e.g., aneurysm clip) or interfere with an implanted device (e.g., cardiac pacemaker). Standard protocols have been developed at the University of Pennsylvania to ensure that subjects at risk do not undergo an MRI scan. This protocol includes an extensive checklist that is completed by the subject or family member; additionally, the MRI technician interviews subjects prior to entering the MRI suite. A second potential concern comes from loose metallic objects in the MRI suite that can serve as missiles if they are drawn to a powerful magnet. Metallic objects that are not secured to the floor or wall are not permitted in the MRI suite. We note that these procedures have been employed in the clinical and research settings at the University of Pennsylvania for many years; no adverse effects from MRI scanning have been experienced to date. Subjects who are or think they might be pregnant will be excluded because the safety of MRI in pregnancy has not been established. The major risk from CAT scan is a small dose of ionizing radiation. This procedure has been approved by the Penn IRB and subjects will be asked to sign a consent form in which the potential risks are discussed.

TMS: The following steps will be taken to minimize risks from TMS identified above.

1. We will use train durations and stimulus intensities that fall within the guidelines recommended by the NIH consensus meeting (see 127).
2. Subjects will be monitored during and after TMS stimulation for involuntary movements that could represent focal motor seizures. Should suspicious motor activity be observed or a change in level of responsiveness occur, the session will be terminated and the subject withdrawn from the study.
3. A physician will be available by phone during all site-finding and whenever TMS is being delivered.
4. All subjects will wear foam earplugs during testing sessions.
5. In the unlikely event that a seizure is observed, the subject will be evaluated by a physician within minutes. In the entire experience with TMS throughout the world, we are unaware of any reports of seizures that were not self-limited; because of this we do not anticipate giving medications. In the event of a seizure, subjects will be asked to undergo an EEG and a MRI scan and may be asked to stay in the hospital overnight for observation.

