6.4.5 Visit 18, 19 & 20 (12-week follow-up)

The same battery of tasks administered in visits 1 and 2 will be administered in these visits, which will occur at 12 weeks after the end of TMS. The anticipated time of these visits is 120-180 minutes. Additionally, for those subjects who had an MRI at the beginning of the study, a repeat MRI scan

The 12-week follow-up visits may be conducted via tele-assessment.

For in-person follow-up visits (i.e. not conducted via tele-assessment), the final day of the follow-up testing may include a brief tele-assessment, time permitting and with the subjects approval. This tele-assessment will consist of some combination of the tests (listed under Visits 1 and 2) conducted via video software; study personnel will conduct this tele-assessment from a nearby room.

6.6 *Subject Withdrawal*

Patients are free to withdraw from the study at any time if they no longer wish to participate. Additionally, patients may be withdrawn from the study prior to the expected completion date for a number of reasons:

- 1) Any adverse outcome or event which may represent a possible health risk to the patient
- 2) Failure of the patient to adhere to protocol requirements

3) Worsening of motor strength, language abilities, or worsening cognition or mood. Abrupt discontinuation of TMS is not associated with rebound effects or other adverse outcomes, so no alternative treatment or transitional therapy will be required if patient discontinue the protocol.

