6.6.1 Data Collection and Follow-up for Withdrawn Subjects

Some patients may wish to stop receiving TMS per the protocol. In this case, attempts will be made to obtain permission to continue collecting data from motor and cognitive testing in a way that mirrors patients who are receiving TMS as specified by the protocol. Should patients wish to withdraw from the study entirely, attempts will be made to seek permission to obtain survival data on such patients throughout the protocol defined follow-up period. It will be a high priority to try to obtain at least survival data on all patients lost to follow-up. A number of attempts will be made to contact a patient by various means before he or she will be considered lost to follow-up. These methods will consist of three or more of phone calls to patient, followed by a phone call to next-of-kin if possible, followed by a certified letter. Should all of these efforts fail to elicit a response the patient will be considered lost to follow-up.

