6.7 Early Termination Visits

All subjects that decide to leave the study early or are asked to by the investigator will be strongly encouraged to continue follow-up visits, but early termination visits are not planned.

7 Study Evaluations and Measurements

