9.6 Stopping Rules

The trial may be stopped for safety concerns or poor study performance, including failure to recruit and/or retain subjects. Subjects who report significant discomfort from TMS, seizure, or worsening of language or cognition during TMS will remain in the study with treatment discontinuation. Two sources of information about short-term adverse effects of TMS on language function will be available. First, subjects and family will be asked if they see evidence of deterioration in language or other faculties each day they return for TMS. Second, the SLP will see the subject during each treatment session. S/he will be instructed to inform the PI if s/he observes a clinically significant worsening in language function. If the SLP is concerned, the WAB will be repeated. If this supports a decline from baseline (operationally defined as more than 5 points below baseline), the adverse effect will be reported and the subject will be withdrawn from treatment. In order to support the intention-to-treat analysis, all such subjects will be strongly encouraged to continue follow-up.

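### Section 12.1.2 withdraws subjects with possible seizure signs from the study, while 9.6 keeps subjects with seizure in it and stops only TMS; aligning the wording, and the worsening reason in 6.6, is a cheap, minor protection of intent-to-treat follow-up

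*Combined protocol and SAP*

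**What the plan says.** Three places in the protocol deal with a subject who runs into trouble during or after TMS.

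- **Section 12.1.2 (TMS, step 2).** Subjects are watched for involuntary movements that might be focal motor seizures. If such movements or a change in responsiveness occur, "the session will be terminated and the subject withdrawn from the study".
- **Section 9.6.** Subjects who report significant discomfort, seizure or "worsening of language or cognition during TMS will remain in the study with treatment discontinuation". The section then describes a repeat WAB when the speech-language pathologist is concerned. A fall of more than 5 points below baseline leads to withdrawal from treatment, followed by: "In order to support the intention-to-treat analysis, all such subjects will be strongly encouraged to continue follow-up".
- **Section 6.6.** Here "patients may be withdrawn from the study prior to the expected completion date for a number of reasons". One listed reason is "Worsening of motor strength, language abilities, or worsening cognition or mood"; another is "Failure of the patient to adhere to protocol requirements".

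Two further sections bear on what happens next. Section 6.6.1 opens with "Some patients may wish to stop receiving TMS per the protocol" and seeks permission to continue testing those patients. Section 6.7 covers all subjects who choose to leave or who "are asked to by the investigator will be strongly encouraged to continue follow-up visits", and adds that no early termination visits are planned.

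On the analysis side, 8.5 takes the randomized population. Section 8.4.1 specifies an intent-to-treat linear mixed model on the 3- and 6-month WAB-AQ changes, with sensitivity analyses for data missing not at random.

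**The concern.** An intent-to-treat analysis needs outcome data on every randomized subject, including those whose stimulation was stopped. Section 9.6 separates stopping treatment from leaving the study and gives the analysis as its reason. Section 12.1.2 merges the two for an overlapping event. A site following 12.1.2 literally could record a subject as off study and not schedule the 3- and 6-month WAB.

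The worsening reason in 6.6 raises the same issue more directly, because worsening language is related to the quantity the trial measures. Nor is it confined to the treatment period, which is all that the 9.6 rule covers.

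At stake are a few avoidable missing outcomes. Some could be related to arm, since subjects in the sham group never receive TMS and seizure signs are therefore more likely under active stimulation.

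**Working it through.** **The instructions side by side**

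| Section | Trigger | Instruction | Follow-up wording |
|---|---|---|---|
| 12.1.2 | Observed suspicious movement or changed responsiveness | Off the study | None; no cross-reference |
| 9.6 | Reported discomfort, seizure or worsening during TMS | Stays in the study, TMS stopped | Strongly encouraged, stated for subjects taken off treatment after a WAB decline |
| 6.6 | Worsening motor, language, cognition or mood, at any time | May leave the study | None in 6.6 itself |
| 6.7 | Any early leaver, including at the investigator's request | Not applicable | Strongly encouraged |

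1. The triggers in 12.1.2 and 9.6 are not identical: one is observed signs, the other reported events. They overlap on seizure. A seizure that staff see and the subject reports falls under both, with opposite instructions on study status, and nothing says which governs.
2. Read literally, a suspected event takes the subject off study while a reported seizure does not. That ordering is unlikely to be intended.
3. Worsening during TMS is mandatory to retain under 9.6 but optional to withdraw under 6.6. After the treatment weeks, only 6.6 and 6.7 apply.
4. Section 6.7 reaches subjects removed under 12.1.2 or 6.6, so the plan still seeks their follow-up. What differs is status: visits kept on the schedule, or visits encouraged after a withdrawal.

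**The plan's own power figure**

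Inputs from 8.3: difference 0.7 SD, 75 evaluable subjects at 2:1 (50 TMS, 25 sham), alpha 0.05, two-sample t-test. Two-sided testing is assumed, because 8.3 does not state it.

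- Sham-arm size = (1 + 1/2)(1.960 + 0.842)² / 0.7² = 1.5 × 7.85 / 0.49 = 24.03, rounded up to 25; total 75. The plan's figure reproduces.
- Noncentrality = 0.7 / √(1/50 + 1/25) = 0.7 / 0.2449 = 2.86 on 73 degrees of freedom. Exact power is 80.5%, against the stated 80%.

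**Effect of one lost subject (assumed number)**

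- 49 versus 25: noncentrality = 0.7 / √(1/49 + 1/25) = 2.85; power 80.2%, a fall of 0.3 percentage points.
- Section 8.3 recruits up to 83 to keep 75, an allowance of 83 − 75 = 8. One such withdrawal can fall inside that allowance, and the power loss would then be nil.

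**Bias**

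A figure would need the number lost, the split by arm and the relation of the loss to 6-month change. The documents give none of these.

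**The case against.** The strongest reply is that the consequence is already handled. Section 6.7 gives investigator-removed subjects the same strong encouragement that 9.6 gives, and 8.5 analyses everyone randomized. On that reading, only terminology in a risk section is left. Most of this stands, and it is why the point is minor. It does not remove the contradiction: 12.1.2 refers to neither 6.7 nor 9.6, and encouraging visits after telling a subject they are withdrawn is a weaker instruction than keeping them on the schedule. The sensitivity analyses in 8.4.1 can probe the effect of missing scores but cannot recover them.

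Three stronger readings are tempting, and the documents support none of them.

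- **A reader might infer a measurable bias in favour of TMS.** Suppose 4 of 50 TMS subjects and no sham subjects are lost through worsening, early worsening correlates 0.5 with 6-month change, and no follow-up is obtained. A simulation with no true effect then gives about 0.45 WAB-AQ points. With losses in proportion across arms (2 and 1, or 4 and 2), the same model gives 0.01 to 0.02. The one-arm assumption produces the result. Section 5.3 blinds the speech-language pathologist and the language assessors, so under no effect they would see worsening in both arms.
- **A reader might use 12.1.1 to bound the event rate.** That section says no aphasic subject among over 250 was reported to have withdrawn for adverse effects. Reported withdrawals are not the 12.1.2 trigger, which is any suspicious movement or change in responsiveness, so the figure does not bound it.
- **A reader might infer that 6.6 and 6.6.1 leave other withdrawn subjects without follow-up and need rewriting.** Section 6.7 covers those subjects, 8.5 already encourages follow-up of non-compliant subjects, and 6.6.1 seeks at least survival data on all patients lost to follow-up.

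**Conclusion.** The point holds as a minor inconsistency. Section 12.1.2 conflicts with 9.6 on the study status of a subject with seizure, and 6.6 permits study withdrawal for worsening that 9.6, during TMS, says should not end participation. The rule in 9.6 is the one consistent with 8.4.1 and 8.5.

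The expected effect on bias and power is very small. This rests on 6.7 being applied in practice, on the trigger being uncommon (12.1.2 calls an observed seizure unlikely but gives no rate), and on the planned sensitivity analyses. The 0.3-point fall in power is an illustration for one assumed loss, not a forecast. No numeric bias is claimed. The clinical criteria for stopping stimulation are not questioned.

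**What to change.** In 12.1.2, state that the session ends and the subject is withdrawn from TMS, remaining in the study for the 3- and 6-month assessments, with a cross-reference to 6.7 and 9.6. Because 12.1.2 also serves the Alzheimer sub-study, add its 6- and 12-week assessments.

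Make the same change for the worsening reason in 6.6. Allow two exceptions in both places: the subject withdraws consent, or a specific follow-up procedure is judged unsafe, in which case only that procedure is skipped. The other reasons in 6.6, and 6.6.1, can stay as they are.

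This is a cheap improvement: protocol wording only, with no change to sample size, endpoint or model. The downside is a few follow-up visits that 6.7 and 9.6 already request.

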12.2 Benefits

The objective of the study is to determine if TMS paired with CILT improves chronic aphasia; subjects randomized to the TMS+CILT treatment group may benefit from the treatment. We note that the study is also potentially of benefit to those who randomize to the sham TMS+CILT group as they will receive two weeks of CILT, an accepted form of speech therapy for which there is evidence of efficacy. The study is also of potential benefit to other subjects with chronic aphasia as it may identify an effective therapy for this disabling condition.

12.3 AD Sub-Study Benefits

The objective of the sub-study is to determine if TMS paired with CILT improves verbal communication in AD; subjects randomized to the TMS+CILT treatment group may benefit from the treatment. We note that the study is also potentially of benefit to those who randomize to the sham TMS+CILT group as they will receive two weeks of CILT, an accepted form of speech therapy for which there is evidence of efficacy. The study is also of potential benefit to other subjects with AD as it may identify an effective therapy for impaired verbal communication.

